### **1.1.2.2. Clinical Efficacy of Ibrutinib in Waldenström's Macroglobulinemia**

Three clinical studies within the clinical development program have enrolled subjects with WM. Efficacy results are summarized as below.

#### **1.1.2.2.1. Study PCYC-04753**

Study PCYC-04753 is a Phase 1, dose-escalating study of ibrutinib in subjects with recurrent B-cell lymphoma.

The study enrolled 4 male subjects with relapsed/refractory WM who received a median of 3 prior systemic regimens and were treated at 2 different dose levels (560 mg/day and 12.5 mg/kg/day). One out of the 4 subjects achieved disease stabilization according to the treating physician but ultimately discontinued ibrutinib due to progressive disease after 8 months. Three out of the 4 subjects achieved a PR (IgM reduction of at least 50% from baseline). The induced responses were durable, and all 3 subjects rolled over onto the extension Study PCYC-1103-CA and continue to receive treatment with ibrutinib for more than 4 years. In addition to the clinically significant IgM decrease in the 3 responders, all 4 subjects had an increase in their hemoglobin and hematocrit over treatment time.

#### **1.1.2.2.2. Study PCYC-1118E**

Study PCYC-1118E is a Phase 2, single-arm, multi-center study designed to evaluate the safety and efficacy of ibrutinib in subjects with WM. Treatment was comprised of ibrutinib administered orally at a daily dose of 420 mg and continued for approximately 3 years or until disease progression. Sixty-four (64) subjects were enrolled; at the time of the data cutoff, efficacy data were obtained from 63 subjects. The median time on study was 14.8 months.

The clinical response rate (MR or better) was 87.3% and the response rate (PR or better) was 69.8%, respectively; the responses were rapid, durable, improved over time, and were associated with sustained improvements in hemoglobin. The median progression-free survival (PFS) was

not reached. The estimated 18-month landmark PFS rate was 83.2%. The median OS was not reached. The estimated 18-month landmark OS rate was 81.7%.

#### **1.1.2.2.3. Study PCYC-1127-CA**

The Phase 3 Study PCYC-1127-CA is a randomized, double-blind, placebo-controlled study to evaluate safety and efficacy of ibrutinib in combination with rituximab in subjects with WM. In addition, an open-label substudy is included to further investigate the safety and efficacy of ibrutinib monotherapy in subjects with WM who were considered refractory to the last prior rituximab-containing therapy.

In the randomized study, 150 subjects were randomized in a 1:1 ratio to receive ibrutinib and rituximab (Ibr+R) or placebo and rituximab (Pbo+R). The median time on study was 26.5 months at the time of the primary analysis (26.7 months for the Ibr+R arm and 26.0 months for the Pbo+R arm). Analysis of PFS per the Independent Review Committee [IRC] demonstrated a statistically significant reduction in the risk of disease progression or death in the Ibr+R arm compared to the Pbo+R arm (HR=0.202,  $p<0.0001$ ). The response rate (PR or better) per IRC assessment was significantly higher for the Ibr+R arm (72.0%) than the Pbo+R arm (32.0%) ( $p < 0.0001$ ).

Thirty-one (31) subjects were enrolled in the open-label ibrutinib monotherapy substudy, all of whom received ibrutinib and comprised the population used for efficacy analyses. The median time on study was 34.4 months. Efficacy results show that ibrutinib 420 mg once daily is highly active for subjects with rituximab refractory WM. Median PFS per IRC assessment was not reached; the 30-month landmark estimate was 57.5%. The response rate (PR or better) per IRC assessment was 71.0%.

A summary of efficacy results for Studies PCYC-1118E and PCYC-1127-CA is provided in [Table 1](#).

**Table 1: Efficacy Results with Ibrutinib in subjects with WM**

Study	Description	No. of Subjects	Efficacy Results a
PCYC-1118E	Phase 2, open-label, single-arm, monotherapy, multicenter study in subjects with previously treated WM	63	
Median time on study: 14.8 months
 
PFS (INV)c: 83.2% (95% CI: 66.3, 92.1) at 19 months, median NR
 
PFS (IRC): 79.5% (95% CI: 65.8, 88.2)
 
ORR (INV)b: 87.3% (95% CI: 76.5, 94.4)
 
ORR (IRC): 82.5% (95% CI: 70.9, 90.9)
 
Major response rate (INV)c: 69.8% (95% CI: 57.0, 80.8)
 
Major response rate (IRC): 61.9% (95% CI: 48.8, 73.9)
 
Median DOR (INV)c: NR
 
OSc: 81.7% at 18 months, median NR

PCYC-1127-CA	Phase 3, randomized, double-blind, placebo-controlled, combination therapy, multicenter study in subjects with WM.	
Randomized study:
 
75 ibrutinib +R
 
75 placebo +R
	
Median time on study: 26.7 months Ibr+R
 
26.0 months Pbo+R
 
PFS (IRC)b: HR 0.20 (95% CI: 0.11, 0.38), p<0.0001
 
PFS (INV): HR: 0.22 (95% CI: 0.12, 0.40), p<0.0001
 
Median PFS (IRC)b: NR ibrutinib+R vs. 20.3 months placebo+R
 
Median PFS (INV): NR ibrutinib+R vs. 20.3 months placebo+R
 
ORR (IRC)c: 72.0% ibrutinib+R vs. 32.0% placebo+R
 
ORR (INV): 77.3% ibrutinib+R vs. 33.3% placebo+R
 
Median TTnT (IRC): NR ibrutinib+R vs. 18.1 months placebo+R
 
OSc: 93.7% ibrutinib+R vs. 91.9% placebo+R at 30 months, median NR for either arm

			
Median time on study: 34.4 months ibrutinib arm
 
Open-label substudy:
 
31 ibrutinib single agent treatment
 
PFS (IRC): 57.5% (95% CI: 38.2, 72.7) at 30 months, median NR
 
PFS (INV): 64.4% (95% CI: 44.9, 78.4) at 30 months, median NR
 
ORR (IRC): 71.0%
 
ORR (INV): 77.4%
 
OS: 90.3% at 30 months, median NR

Abbreviations: CI=confidence interval; DOR=duration of response; HR=hazard ratio; IRC= Independent Review Committee; NR= not reached; ORR=overall response rate; OS=overall survival; PFS=progression-free survival.

a. Efficacy results are based on the primary analysis for Studies PCYC-1118E and PCYC-1127-CA.

b. Primary endpoint

c. Secondary endpoint.

### **1.1.2.3. Clinical Safety of Ibrutinib**

As of 12 November 2019, safety data from completed studies (primary or final analysis clinical study reports [CSRs] completed) are available for 4,439 subjects. Of these, 2,132 subjects were exposed to ibrutinib in monotherapy trials (1,600 subjects with hematologic malignancies, 42 subjects with cGVHD, 460 healthy volunteers, and 30 subjects in a hepatic impairment study) and 2,307 subjects were exposed to ibrutinib in combination therapy trials (1,971 subjects with hematologic malignancies, and 336 subjects with solid tumors). A brief overview of the potential risks associated with the administration of ibrutinib based on sponsor-initiated clinical studies is presented in the ibrutinib Investigator's Brochure and is outlined below.

#### **1.1.2.3.1. Non-Hematological Adverse Events**

##### ***Bleeding-Related Events***

There have been reports of bleeding events in subjects treated with ibrutinib, both with and without thrombocytopenia. These include minor bleeding events such as contusion, epistaxis, and petechiae; and major bleeding events, some fatal, including gastrointestinal bleeding, intracranial hemorrhage, and hematuria.

In an in vitro platelet function study, inhibitory effects of ibrutinib on collagen induced platelet aggregation were observed. Use of either anticoagulant or antiplatelet agents concomitantly with ibrutinib increases the risk of major bleeding. A higher risk for major bleeding was observed with anticoagulant than with antiplatelet agents. Consider the risks and benefits of anticoagulant or antiplatelet therapy when co-administered with ibrutinib. Monitor for signs and symptoms of bleeding.

See Section 8.2.3 for guidance on concomitant use of anticoagulants, antiplatelet therapy and/or supplements. See Section 8.4 for guidance on ibrutinib management with surgeries or procedures.

##### ***Infections***

Infections (including sepsis, bacterial, viral, or fungal infections) were observed in subjects treated with ibrutinib therapy. Some of these infections have been associated with hospitalization and death. Consider prophylaxis according to standard of care in subjects who are at increased risk for opportunistic infections. Although causality has not been established, cases of progressive multifocal leukoencephalopathy and hepatitis B reactivation have occurred in subjects treated with ibrutinib.

##### ***Cardiac arrhythmias***

Atrial fibrillation, atrial flutter, and cases of ventricular tachyarrhythmia including some fatal events, have been reported in subjects treated with ibrutinib, particularly in subjects with cardiac risk factors, hypertension, acute infections, and a previous history of cardiac arrhythmia.

***Interstitial lung disease***

Cases of interstitial lung disease (ILD) have been reported in subjects treated with ibrutinib.

***Non-melanoma skin cancer***

Non-melanoma skin cancers have occurred in subjects treated with ibrutinib.

***Tumor lysis syndrome***

Tumor lysis syndrome has been reported with ibrutinib therapy. Subjects at risk of tumor lysis syndrome are those with high tumor burden prior to treatment.

***Hypertension***

Hypertension has been commonly reported in subjects treated with ibrutinib.

***Cerebrovascular Accidents***

Although causality has not been established, cases of cerebrovascular accident, transient ischemic attack, and ischemic stroke including fatalities have been reported with the use of ibrutinib in the post-marketing setting, with and without concomitant atrial fibrillation and/or hypertension.

***Diarrhea***

Diarrhea is the most frequently reported non-hematologic AE with ibrutinib monotherapy and combination therapy. Other frequently reported gastrointestinal events include nausea, vomiting, and constipation. These events are rarely severe and are generally managed with supportive therapies including antidiarrheals and antiemetics.

***Rash***

Rash has been commonly reported in subjects treated with either single agent ibrutinib or in combination with chemotherapy. In a randomized Phase 3 study (PCYC-1112-CA), rash occurred at a higher rate in the ibrutinib arm than in the control arm. Most rashes were mild to moderate in severity. Isolated cases of severe cutaneous adverse reactions (SCARs) including Stevens-Johnson syndrome (SJS) have been reported in subjects treated with ibrutinib. In addition, hypersensitivity-related events of erythema, urticaria, angioedema have been reported.

**1.1.2.3.2. Hematological Adverse Events*****Cytopenias***

Treatment-emergent Grade 3 or 4 cytopenias (neutropenia, thrombocytopenia, and anemia) were reported in subjects treated with ibrutinib.

***Leukostasis***

There were isolated cases of leukostasis reported in subjects treated with ibrutinib. A high number of circulating lymphocytes ( $>400,000/\text{mcL}$ ) may confer increased risk. Consider temporarily holding ibrutinib.

### **Lymphocytosis**

Upon initiation of single agent treatment with ibrutinib, a reversible increase in lymphocyte counts (ie,  $\geq 50\%$  increase from baseline and an absolute count  $> 5,000/\text{mCL}$ ), often associated with reduction of lymphadenopathy, has been observed in most subjects (66%) with CLL/SLL. This effect has also been observed in some subjects (35%) with MCL treated with ibrutinib.

When ibrutinib was administered in combination with BR or with obinutuzumab in subjects with CLL/SLL, lymphocytosis was infrequent (7% with ibrutinib + BR versus 6% with placebo + BR and 7% with ibrutinib + obinutuzumab versus 1% with chlorambucil + obinutuzumab).

Lymphocytosis was not observed in subjects with WM treated with ibrutinib.

#### **1.1.2.3.3. Long-term safety**

The long-term safety data over 5 years from 1,178 subjects (treatment naïve CLL/SLL n = 162, relapsed/refractory CLL/SLL n = 646, and relapsed/refractory MCL n = 370) treated with ibrutinib were analyzed. The median duration of treatment for CLL/SLL was 51 months (range, 0.2 to 98 months) with 70% and 52% of subjects receiving treatment for more than 2 years and 4 years, respectively. The median duration of treatment for MCL was 11 months (range, 0 to 87 months) with 31% and 17% of subjects receiving treatment for more than 2 years and 4 years, respectively. The overall known safety profile of ibrutinib-exposed subjects remained consistent, other than an increasing prevalence of hypertension, with no new safety concerns identified. The prevalence for Grade 3 or greater hypertension was 4% (year 0-1), 6% (year 1-2), 8% (year 2-3), 9% (year 3-4), and 9% (year 4-5). The incidence for the 5-year period was 11%.

### **1.2. Overall Rationale for the Study**

WM is a malignant B-cell lymphoma that is associated with an accumulation of clonal lymphoplasmacytic cells and monoclonal IgM secretion. Although treatments such as chemotherapy or chemoimmunotherapy has shown some activity in subjects with WM, more effective therapeutic options still need to provide long term disease control with reduced toxicity especially for those who do not respond to rituximab-based treatment.

Ibrutinib is an orally administered, small-molecule inhibitor of BTK. In contrast to the traditional therapeutic agents, it can trigger apoptosis of WM cells with MYD88L265P which present in more than 90% of subjects. Studies PCYC-1118E and PCYC-1127-CA demonstrated that ibrutinib is highly effective and has a favorable safety profile for the treatment of WM, which leads to the conditional approval of ibrutinib in WM in China. Since no Chinese subjects were enrolled in the global pivotal studies, this single arm, multicenter, Phase 4 study is to evaluate the efficacy and safety of ibrutinib monotherapy in Chinese subjects with relapsed or refractory WM. As agreed upon with the China NMPA, data from this study will be used to support the full approval for ibrutinib in WM in China.

## 2. OBJECTIVES, ENDPOINTS, AND HYPOTHESES

### 2.1. Objectives and Endpoints

#### 2.1.1. Objectives

##### Primary Objective

The primary objective of this study is to evaluate the efficacy of ibrutinib based on overall response rate (ORR [PR or better]) by investigator assessment per the modified Consensus Response Criteria from the VIth International Workshop on WM (IWWM) (NCCN 2019), in Chinese subjects with relapsed or refractory WM.

##### Secondary Objectives

Secondary objectives are to evaluate: clinical response rate (minor response [MR] or better) by investigator assessment according to the modified VIth IWWM (NCCN 2019) criteria, Very Good PR (VGPR) or better by investigator assessment according to the modified VIth IWWM (NCCN 2019) criteria; duration of response (DOR) by investigator assessment; time to response (TTR) by investigator assessment; PFS by investigator assessment; overall survival (OS); safety and PK of ibrutinib in Chinese patients with relapsed or refractory WM.

#### 2.1.2. Endpoints

##### Primary Endpoint

The primary efficacy endpoint is ORR by investigator assessment. ORR is defined as the proportion of subjects who achieve PR or better per the modified Consensus Response Criteria from the VIth IWWM (NCCN 2019).

##### Secondary Endpoints

###### Efficacy

- Clinical response rate (CRR,  $\geq$ MR)
- VGPR or better rate
- DOR
- TTR
- PFS
- OS

###### Pharmacokinetics

- To evaluate PK of ibrutinib in Chinese subjects with relapsed or refractory WM

###### Safety

- To assess the safety and tolerability of ibrutinib in Chinese symptomatic relapsed or refractory WM subjects

Refer to Section 9, Study Evaluations for evaluations related to endpoints.

## 2.2. Hypothesis

The primary hypothesis for this study is that ibrutinib is an effective agent as measured by ORR (with a point estimate approximately 70% and the lower bound of the 90% confidence interval [CI] is greater than 32%) in Chinese subjects with relapsed/refractory WM.

## 3. STUDY DESIGN AND RATIONALE

### 3.1. Overview of Study Design

This is a single-arm multicenter, Phase 4 study to evaluate the efficacy and safety of ibrutinib in Chinese subjects with relapsed or refractory WM with symptomatic disease meeting at least 1 of the recommendations from the Second IWWM for requiring treatment.

Approximately 17 subjects will be enrolled into the study. Subjects will receive ibrutinib 420 mg daily until disease progression or unacceptable toxicity, whichever occurs first. Ibrutinib will be supplied as hard gelatin capsules for oral administration.

The study will include a Screening Phase, a Treatment Phase and a Follow-Up Phase.

The Screening Phase assessments will be performed within 30 days prior to study treatment and will begin on the day the subject signs informed consent. During the Screening Phase, the subjects' eligibility will be determined.

The Treatment Phase will extend from first dose of study drug until study drug discontinuation.

[figure not shown]
The Follow-up Phase will consist of the Post-treatment pre-disease progression Phase and a Post-disease Progression Phase. The Post-treatment pre-disease progression Phase will extend from the discontinuation of treatment (for reasons other than disease progression) until the subject has progressive disease, at which point the Post-disease Progression Phase will begin. Subjects who progress on treatment will transition directly to the post disease progression phase. In this latter phase, subsequent anticancer therapy, occurrence of any other malignancy and survival status will be recorded until death, lost to follow-up, consent withdrawal, or study closure.

The study is planned to be completed 3 years after the last subject receives first dose.

Clinical cutoffs (CCOs) planned for this study are:

- CCO for the primary analysis is estimated to be performed approximately 12 months after the last subject receives first dose. Alternative appropriate cutoffs will be considered based on regulatory requirement.
- CCO for the final analysis is estimated to occur 3 years after last subject receives first dose.

A diagram of the study design is provided in [Figure 1](#).

**Figure 1: Schematic Overview of the Study**

### 3.2. Study Design Rationale

#### 3.2.1. Rationale for Ibrutinib Dose

The proposed dose for ibrutinib is 420 mg per day (3 × 140-mg capsules) administered once daily without interruption. In Study1118E and Study 1127, the 420 mg dose administered once daily appeared safe and favorable responses were seen in subjects with previously treated WM as outlined in Section 1.1.2.2.

#### 3.2.2. Rationale for Efficacy Endpoints

The proposed study uses ORR as the primary endpoint, since it has already served as the basis for regulatory approvals in WM. Key secondary endpoints such as DOR are also recommended endpoints for the clinical study evaluation of new treatments for WM.

## 4. SUBJECT POPULATION

### 4.1. Inclusion Criteria

Each potential subject must satisfy all of the following criteria to be enrolled in the study:

1. Men and women  $\geq 18$  years of age.
2. Eastern Cooperative Oncology Group (ECOG) performance status grade of  $\leq 2$ .
3. Subjects must have received at least one prior therapy for WM and have had either documented disease progression or had no response (stable disease) to the most recent treatment regimen.
4. Centrally confirmed clinicopathological diagnosis of WM in accordance with the consensus panel of the Second IWWM.

Note: Bone marrow aspirate and biopsy should be performed for all subjects at screening and should be completed within 30 days of first dose administration. Samples will be sent to the central laboratory to confirm clinicopathological diagnosis of WM.

5. Measurable disease defined as serum monoclonal IgM  $>0.5$  g/dL.
6. Symptomatic disease meeting at least 1 of the criteria from the Second IWWM for requiring treatment.
  - a. Constitutional symptoms documented in the subject's chart with supportive objective measures, as appropriate, defined as one or more of the following disease-related symptoms or signs:
    - i. Unintentional weight loss  $\geq 10\%$  within the previous 6 months prior to Screening
    - ii. Fevers higher than 100.5°F or 38.0°C for 2 or more weeks prior to Screening without evidence of infection
    - iii. Night sweats for more than 1 month prior to Screening without evidence of infection
  - b. Clinically relevant fatigue which is not relieved by rest due to WM
  - c. Symptomatic hyperviscosity or serum viscosity levels greater than 4.0 centipoises (or in equivalent units)
  - d. Lymphadenopathy which is either symptomatic or bulky ( $\geq 5$  cm in maximum diameter)
  - e. Symptomatic hepatomegaly and/or splenomegaly and/or organ tissue infiltration
  - f. Peripheral neuropathy due to WM

- g. Symptomatic cryoglobulinemia
- h. Cold agglutinin anemia
- i. IgM related immune hemolytic anemia and/or thrombocytopenia
- j. Nephropathy related to WM
- k. Amyloidosis related to WM
- l. Hemoglobin  $\leq 10$  g/dL
- m. Platelet count  $< 100 \times 10^9$ /L
- n. Serum monoclonal protein  $> 6$  g/dL, with or without overt clinical symptoms

7. Meet the following laboratory parameters:

- a. Absolute neutrophil count  $> 750$  cells/mm $^3$  ( $0.75 \times 10^9$ /L) independent of growth factor support within 7 days of the laboratory testing
- b. Platelet count  $> 50,000$  cells/mm $^3$  ( $50 \times 10^9$ /L) without transfusion support within 7 days of the laboratory testing
- c. Hemoglobin  $\geq 7$  g/dL without transfusion or growth factor support within 7 days of the laboratory testing
- d. Serum aspartate transaminase (AST) or alanine transaminase (ALT)  $< 3.0 \times$  upper limit of normal (ULN).
- e. Estimated Creatinine Clearance using Cockcroft Gault  $\geq 30$  mL/min (see [Attachment 6](#)).
- f. Total bilirubin  $\leq 1.5 \times$  ULN (unless bilirubin rise is due to Gilbert's syndrome or of nonhepatic origin).
- g. Prothrombin time (PT)/international normalized ratio (INR)  $\leq 1.5 \times$  ULN and PTT (aPTT)  $\leq 1.5 \times$  ULN unless abnormality is unrelated to a coagulopathy or bleeding disorder.

8. Female subjects of childbearing potential must have a negative serum pregnancy test at Screening and agree to use highly effective methods of contraception while taking study drug. Those using hormonal methods of birth control must add a barrier method. Female subjects of childbearing potential should avoid becoming pregnant while taking ibrutinib and for up to 1 month after the last dose of study drug.

9. Male subjects must use an effective barrier method of contraception during the study and for 3 months following the last dose of ibrutinib if sexually active with a female of childbearing potential.

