### Existing Therapies in WM

Treatment for WM is recommended only for symptomatic disease. Currently in China, WM is treated most often with rituximab as a monotherapy or in combination with chemotherapy. These regimens have shown activity, however, none of these options is curative and a standard of care has not been established. Short-term- and long-term toxicities caused by traditional therapeutic agents (such as chemotherapy or chemoimmunotherapy) make these treatments challenging for patients with WM who are generally aged 65 years and older and often have comorbidities. Furthermore, present treatment approaches for relapsed WM provide a modest progression-free survival of 16–24 months in the second-line and third-line settings. More effective therapeutic options therefore are needed to provide long-term- disease control with reduced toxicity.

Ibrutinib is an orally administered, small-molecule inhibitor of Bruton's tyrosine kinase (BTK). Unlike traditional therapeutic agents, it can trigger apoptosis of WM cells with MYD88 (Leu265Pro) which is present in more than 90% of WM patients. Additionally, ibrutinib inhibits HCK, an SRC family member that is transactivated by mutated MYD88 and triggers both AKT and extracellular-signal-regulated kinase (ERK) prosurvival signaling in WM cells. Studies PCYC-1118E and PCYC-1127-CA demonstrated clinical benefit as well as a favorable safety profile of ibrutinib in subjects with WM. Based on the results of these two studies, China National Medical Product Administration (NMPA) conditionally approved ibrutinib in WM in November 2018, making ibrutinib the first drug specifically approved for the treatment of this rare disease in China.

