### **1.1.2.1. Human Pharmacokinetics**

The PK of ibrutinib has been assessed in subjects with B-cell malignancies, cGVHD, as well as in healthy subjects. In all studies, both parent ibrutinib and metabolite PCI-45227 were quantified. PCI-45227 is a prominent dihydrodiol metabolite observed in laboratory animals and humans, with a reversible inhibitory activity towards BTK approximately 15 times lower than that of ibrutinib and with plasma concentrations in the same range as parent drug levels. The on target effects of metabolite PCI-45227 are not considered clinically relevant. The PK of ibrutinib does not significantly differ in patients with different B-cell malignancies (CLL, SLL, MCL, WM, and MZL). Ibrutinib is absorbed after oral administration with a median  $T_{max}$  of 1 hour to 2 hours. The half-life of ibrutinib is 4 to 6 hours. Administration of ibrutinib in a fasted condition resulted in approximately 60% of exposure (AUC) as compared to administration either in fed condition (30 minutes after a high-fat breakfast), or 2 hours after a meal. Considering the approximate doubling in mean systemic exposure when dosed with food and the favorable safety profile, ibrutinib can be dosed with or without food. The PK in Chinese CLL/SLL patients is similar to those in non-Chinese subjects with various B-cell malignancies.

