#### **4.3. Prohibitions and Restrictions**

Potential subjects must be willing and able to adhere to the following prohibitions and restrictions during the course of the study to be eligible for participation:

1. Refer to Section 8 for details regarding prohibited and restricted therapy during the study.
2. Agree to follow all requirements that must be met during the study as noted in the Inclusion and Exclusion Criteria (eg, contraceptive requirements).

The following guidance should be applied during the perioperative period for subjects who require surgical intervention or an invasive procedure while receiving study medication:

- For any surgery or invasive procedure requiring sutures or staples for closure, study medication should be held at least 7 days prior to the intervention and should be held at least 7 days after the procedure, and restarted at the discretion of the investigator when the surgical site is reasonably healed without serosanguineous drainage or the need for drainage tubes.
- For minor procedures (such as a central line placement, needle biopsy, thoracentesis, or paracentesis), study medication should be held for at least 3 days prior to the procedure and should not be restarted for at least 3 days after the procedure. For bone marrow biopsies that are performed while the subject is on study medication, it is not necessary to hold study medication for these procedures.
- For emergency procedures, study medication should be held after the procedure until the surgical site is reasonably healed, for at least 7 days after the urgent surgical procedure.

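### Criterion 8 ends women's required contraception at the last dose, although the same criterion asks them to avoid pregnancy for up to 1 month longer

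*Protocol*

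**What the plan says.** Criterion 8 in Protocol Section 4.1 makes three statements about contraception and pregnancy for women of childbearing potential.

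- They must "agree to use highly effective methods of contraception while taking study drug".
- On hormonal contraception: "Those using hormonal methods of birth control must add a barrier method". No period is attached to this rule.
- They "should avoid becoming pregnant while taking ibrutinib and for up to 1 month after the last dose of study drug".

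Criterion 9, for men with a partner of childbearing potential, puts the period on the method itself: "Male subjects must use an effective barrier method of contraception during the study and for 3 months following the last dose of ibrutinib".

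Section 4.3, item 2, makes these requirements a condition of participation ("Agree to follow all requirements that must be met during the study as noted in the Inclusion and Exclusion Criteria (eg, contraceptive requirements"). It only points back to the criteria and adds no period of its own.

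**The concern.** Two periods in one criterion do not match. The sponsor has decided that pregnancy should be avoided for up to 1 month after the last dose, but the obligation to use a highly effective method ends with dosing. The barrier rule for hormonal users has no period of its own and most naturally follows the on-treatment period in the sentence before it, so it ends then too.

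Read literally, a woman could stop the highly effective method, or drop the added barrier, at her last dose and still meet the method requirement while the avoidance period is open. She would still be under the instruction not to conceive, but with no standard for how. What is at stake is a possible fetal exposure inside a window that the protocol itself treats as one to avoid. The response rate and the other analyses are not involved.

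**Working it through.** There is no stated figure to reproduce. The check compares the periods, looks for other text that would close the gap, and then sizes it.

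**1. Periods after the last dose (Section 4.1)**

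| Requirement | Time after last dose | Method named |
|---|---|---|
| Women: highly effective contraception | 0 months | Yes |
| Women: added barrier with hormonal methods | None stated | Yes |
| Women: avoid pregnancy | Up to 1 month | No |
| Men: barrier contraception | 3 months | Yes |

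Gap for women = up to 1 month − 0 months = up to 1 month.

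**2. Other text that might close it**

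- Section 4.3, item 2: refers back to the criteria.
- Time and Events Schedule, footnote e, and Section 9.4.2: a pregnancy test at Screening, and later only if pregnancy is suspected.
- Section 9.1.3: the End-of-Treatment visit falls 30 days (± 7 days) after the last dose, or before new anticancer treatment. No pregnancy test is scheduled there.
- Section 12.3.3: reporting of pregnancies and stopping treatment, not contraception.
- SAP: does not address contraception.

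None of these names a method for women after the last dose.

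**3. How much of the month involves residual drug**

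Section 1.1.2.1 says "The half-life of ibrutinib is 4 to 6 hours".

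- Five half-lives: 5 × 4 = 20 hours, to 5 × 6 = 30 hours.
- A 30-day month: 30 × 24 = 720 hours.
- Share of the month: 20/720 = 2.8%, to 30/720 = 4.2%.

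The half-life is that of ibrutinib itself. The documents do not say how the 1-month period was chosen.

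**4. How many women**

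Section 3.1: "Approximately 17 subjects will be enrolled into the study". The introduction (Existing Therapies in WM) describes patients as "generally aged 65 years and older", although criterion 1 admits women from age 18. The number of women of childbearing potential is not given. Assuming 0 to 3 of 17 (0% to 3/17 = 17.6%), the exposure is 0 × 1 = 0 to 3 × 1 = 3 woman-months, at most, without a required method.

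**The case against.** The best argument against the point is that criterion 8 should be read as a whole. Its third sentence sits in a mandatory criterion, Section 4.3 makes the contraceptive requirements binding, and a sexually active woman told to avoid pregnancy for a month needs some contraception to comply. On that reading only a repeat of the method is missing. The month is also not unsupervised: adverse events are collected to 30 days after the last dose, an End-of-Treatment visit falls at about that time, a suspected pregnancy must be tested, and any pregnancy must be reported within 24 hours. The consent form, which subjects actually read, may state the longer period. Criterion 9 covers a different group with a different method, so its wording alone does not prove an error in criterion 8.

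Much of this stands, and it is why the point carries little weight. It does not remove the gap. The first two sentences use the language of obligation and set a standard; the third is advisory in wording and names no method. The first sentence also states its own end, so this is a rule that stops too early, not a detail left open. The monitoring provisions would detect or report a pregnancy, but they do not require its prevention. Criterion 9 shows only that this protocol can attach a post-dose period to a method when it means to.

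**Conclusion.** The point holds as a minor wording gap with a safety purpose. For up to 1 month after the last dose, women of childbearing potential are asked to avoid pregnancy without any required method. The practical size is very low: 0 to 3 woman-months in the whole study, on an assumed 0 to 3 women of childbearing potential among 17 subjects, a range that the documents neither give nor support. Zero is plausible. On the stated half-life, five half-lives cover only about 3% to 4% of the month. No efficacy, safety or PK analysis changes. Whether any woman would in practice be told to stop at her last dose cannot be settled without the consent form.

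**What to change.** In the first sentence of criterion 8, extend the required use of highly effective contraception so that it covers treatment and the 1 month after the last dose. State that the added-barrier rule for hormonal users applies over the same period. This uses the sponsor's own 1-month figure and the structure already used in criterion 9. Check the consent form and align it if it differs.

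The cost is one phrase plus a short clarification at the next amendment, with a consent-form revision if needed; the change alone does not justify a separate amendment. Editing an entry criterion does not by itself bind women already enrolled, so any affected subject should be told of the longer period directly. The only downside for her is one extra month of required contraception.
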